8.10 Serious Adverse Events (SAE)

A serious adverse event (SAE) defined as one that suggests a significant hazard or side effect, regardless of the investigator or sponsor's opinion on the relationship to the investigational product. This includes, but may not be limited to, any event that:

- Is fatal
- Is life-threatening
- Requires or prolongs (>48 hours) inpatient hospitalization
- Is a persistent or significant disability or incapacity
- Is considered an important medical event

Important medical events may be considered serious by the investigator although they may not be immediately life threatening or result in death or prolong hospitalization. Such important medical events are those that may jeopardize the subject, require intervention to prevent one of the outcomes listed above, or result in urgent investigation. Examples include, but are not limited to, allergic bronchospasm, convulsions, and blood dyscrasias.

Serious Adverse Events will be recorded in the Adverse Event CRF and the event is to be reported by telephone or fax to the Sponsor within 24 hours of knowledge of the event. Sites are also required to adhere to the reviewing IRB requirements for reporting of SAE's.

8.11 Major Adverse Events (MAE)

The following specific events will be considered major adverse events (MAE) for the purpose of evaluating the primary (30 day) and secondary (1 year) safety endpoints:

Major adverse events (MAE) are defined as any one of the following events:

- Death
- Myocardial Infarction
- Stroke (excludes TIA)
- Renal Failure (excludes renal insufficiency)
- Respiratory Failure (excludes COPD or pulmonary complications)
- Paralysis (excludes paraparesis)
- Bowel Ischemia
- Procedural Blood Loss ($\geq 1,000$ cc)

A major adverse event (MAE) may or may not be considered related to the device. Mortality will be reported as "all cause" and "AAA related." All deaths occurring in the first 30 days post-index procedure are considered "AAA related."

The Clinical Events Committee (CEC) shall determine which adverse events are considered Major Adverse Events (MAE) for evaluation of the primary (30 days) and secondary (1 year) safety endpoints.

8.12 Unanticipated Adverse Device Effect (UADE)

An unanticipated adverse device effect means any serious adverse effect on health or safety or any life-threatening problem or death caused by, or associated with, a device, if that effect, problem, or death was not previously identified in nature, severity, or degree of incidence in the investigational plan or application (including a supplementary plan or application), or any other unanticipated serious problem associated with a device that relates to the rights, safety, or welfare of subjects.

Unanticipated Adverse Device Effect (UADE) are to be recorded in the Adverse Event CRF and the event is to be reported by telephone or fax (see above contact information) to the Sponsor within 24 hours of knowledge of the event. Sites are also required to adhere to the reviewing IRB requirements for reporting of any UADE.

8.13 Conversion to Open Surgical repair

Conversion to open surgical repair may occur either at the initial implant procedure or subsequent to the initial procedure. Information regarding the surgical conversion will be recorded on the Open Surgical **Conversion eCRF** and the **Adverse Event eCRF**.

In the event that a subject requires conversion from endovascular to open surgical repair, the explanted device should be sent to TriVascular for examination. Refer to the Manual of

Operations for specific instructions for managing the removal, shipping and handling of the explanted device. Explant information will be recorded on the **Explant eCRF**.

Surgical conversions must be reported by telephone or fax to the Sponsor **within 24 hours** of knowledge of the event.

The Follow-up visit schedule for surgically converted subjects is at one month and one year post open conversion.

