1.0 STUDY GOAL

The goal of this study is to evaluate the performance of the Ovation Abdominal Stent Graft System in subjects with Abdominal Aortic Aneurysms. The specific goals of the study are to:

1. Evaluate the safety of the Ovation Abdominal Stent Graft System at 30, 180, 365-days and annually for 5 years post-implant.
2. Evaluate the ability to deliver the Ovation Abdominal Stent Graft System within the abdominal aorta.
3. Evaluate the ability of the Ovation Abdominal Stent Graft to exclude the abdominal aortic aneurysm.

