6.5 Post-Treatment follow-up period

The following assessments and tests will be performed at the following intervals:

Time period post-treatment	Acceptable visit timeframe allowance
1 Month (30 days)	± 14 days
6 Months (180 days)	± 30 days
12 Months (365 days)	± 60 days
Annually from 2 to 5 years	± 60 days

- Physical exam
- Laboratory testing, which includes renal and optional coagulation assessment
- Contrast Enhanced Spiral Abdominal/Pelvic CT
- Abdominal X-ray (KUB), including AP, lateral, left oblique and right oblique views Device/aneurysm assessment based on imaging (endoleak, migration, integrity, patency, AAA dimensions)
- Concomitant medications (anticoagulants, antiplatelets and antibiotics only)
- Adverse events
- Other relevant data as indicated on the CRF including optional wound assessment.

The above assessments are recorded in the appropriate **Follow-up Visit eCRF**. Note that in the event the subject is unable to tolerate a contrast-enhanced spiral CT, a duplex ultrasound and non-contrast spiral CT should be completed as an alternative assessment.

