8.6 Surgical Conversion

Surgical conversion occurs when a subject implanted with an Ovation Abdominal Stent Graft undergoes open surgical repair with explantation of the stent graft. The follow-up for subjects who are converted to open surgical repair include collection of the following data: Physical Exam and assessment of Adverse Events. The visits are to occur at 1 month post open conversion and 1 year post open conversion.

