10.4.1 Secondary Safety Endpoints

Rates for all-cause mortality, AAA related mortality, major adverse events, AAA rupture, and surgical conversion will all be calculated at 30 days and 12 months. The Kaplan-Meier estimates will be presented with 95% confidence intervals.

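### Planned follow-up of converted subjects ends one year after conversion, short of the 5-year safety goal for any conversion before about day 1400

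*Combined protocol and SAP*

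**What the plan says.** On visits after conversion, Section 8.13 of the combined protocol and SAP states: "The Follow-up visit schedule for surgically converted subjects is at one month and one year post open conversion". Section 8.6 gives the same timing and says that follow-up is to "include collection of the following data: Physical Exam and assessment of Adverse Events". Neither section gives a visit window, and neither says that the index-timed visits run alongside. Section 8.13 allows for any timing: "Conversion to open surgical repair may occur either at the initial implant procedure or subsequent to the initial procedure".

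The safety objectives run on a different clock. The first goal in Section 1.0 reads: "Evaluate the safety of the Ovation Abdominal Stent Graft System at 30, 180, 365-days and annually for 5 years post-implant". Section 10.4.1 says that mortality, AAA-related mortality, major adverse event (MAE), rupture and conversion rates "will all be calculated at 30 days and 12 months", as Kaplan-Meier estimates. Section 6.7 keeps subjects on annual visits to 5 years.

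Conversion does not take a subject out of the study. It is not among the withdrawal reasons in Section 5.3, and the intent-to-treat set in Section 10.8 is fixed by insertion of the delivery system.

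**The concern.** Converted subjects stay in the analysis set, but their planned contacts no longer match the times at which safety is to be evaluated. They are the subjects in whom the device failed and who then had open surgery. Section 9.2.1 itself lists conversion as a route to AAA-related death. If their planned contact ends early, the longer-term safety picture is built mainly from subjects in whom the device stayed in place.

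The 24-hour duties to report deaths and serious adverse events (Sections 8.15 and 8.10) start when the site learns of the event. Without a planned contact, that knowledge is left to chance. Section 6.6 requires unscheduled-visit data only when the visit relates to the device, the procedure or the aneurysm. Information from other visits waits for the next scheduled one. For a converted subject, that may be up to 335 days away (365 - 30), or may never come once the second visit has passed.

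**Working it through.** **Inputs.** Let c be the day of conversion, counted from the index procedure.
- Post-conversion visits: nominally c + 30 and c + 365 (Sections 8.6 and 8.13; no window given).
- Visit allowances: 1 month ± 14 days; 12 months and annual visits ± 60 days (Section 6.5).
- 12-month window: days 305-425 (Section 8.7).
- Primary-phase size: 150 (Section 5.0).

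**1. The plan's own figure.** 365 - 60 = 305 and 365 + 60 = 425, which matches Section 8.7. The 1-month (16-44) and 6-month (150-210) windows also reproduce.

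**2. End of planned follow-up.** The last planned visit is on day c + 365. The year-5 window is 1825 ± 60, or days 1765-1885. Reaching it needs c + 365 ≥ 1765, so c ≥ 1400 (1400/365 = 3.84 years).

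| Conversion day c | Last planned visit |
|---|---|
| 0 | day 365 (year 1) |
| 365 | day 730 (year 2) |
| 730 | day 1095 (year 3) |
| 1095 | day 1460 (year 4) |
| 1400 | day 1765 (start of the year-5 window) |

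**3. Contact in the 12-month window.** On nominal days, neither visit falls in days 305-425 when c + 30 < 305 and c + 365 > 425. That is c = 61 to 274, or 214 days (214/365 = 58.6% of first-year days). The second visit then falls on days 426-639. If the Section 6.5 allowances were applied to the two visits (an assumption, since Sections 8.6 and 8.13 give none), the conditions become c + 44 < 305 and c + 305 > 425. That is c = 121 to 260, or 140 days (38.4%).

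**4. Does this censor the 12-month estimates?** For every c ≥ 0, c + 365 ≥ 365. Each first-year conversion therefore has a planned adverse-event assessment on or after index day 365, at which vital status and dated events up to day 365 can be established. Early censoring needs an analysis run before that visit. The documents give no data cut-off date.

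**5. How often the window is missed.** The documents give neither the rate nor the timing of conversion. As an illustration only, let a share q of first-year conversions occur at the index procedure, with the rest uniform over days 1-365. The share with no contact in the window is (1 - q) × 214/365, or (1 - q) × 140/365 with allowances.

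| q | Nominal days | With allowances |
|---|---|---|
| 0 | 58.6% | 38.4% |
| 0.5 | 29.3% | 19.2% |
| 0.9 | 5.9% | 3.8% |

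**6. Primary endpoints.** Conversion through 12 months is already a treatment failure (Section 9.1.2). For 30-day safety, a conversion on days 0-30 has its first visit on days 30-60, which covers the endpoint.

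**7. Scale.** One subject is 1/150 = 0.67 percentage points of a crude rate.

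**The case against.** The strongest reply is that nobody is dropped. Converted subjects are not withdrawn and remain in the intent-to-treat set. Deaths and serious adverse events are reportable whatever the visit schedule, and the Clinical Events Committee adjudicates them. The conversion itself is reported within 24 hours. Days 305-425 are a visit and imaging window, not an ascertainment window for death or MAE. No planned rate extends beyond 12 months, so the 5-year goal has no stated estimate to distort.

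Much of this stands. A reader might infer that the schedule biases the 12-month Kaplan-Meier estimates in the device's favour as a matter of course. The documents do not support that, because the second visit always falls on or after index day 365. Nor do the literature summaries in Sections 2.1.2 and 2.1.3 settle a direction. Average morbidity is higher for open repair (renal failure 4.2% against 3.0%), but average mortality runs the other way (2.7% open, 3.4% endovascular, the latter described as somewhat inflated by patient selection). These are unweighted averages and do not describe conversions.

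The reply does not dispose of the 5-year point. Section 1.0 states annual safety evaluation to year 5 as a goal, other subjects have visits to meet it, and event reporting depends on the site's knowledge. A general reporting duty does not replace a planned contact.

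**Conclusion.** The point holds as a conflict between Sections 8.6 and 8.13 and the first goal in Section 1.0. Planned contact stops one year after conversion. That is before the year-5 window for any conversion before about day 1400, and at year 1 for a conversion at the index procedure. The effect is selective, because only device failures lose these contacts.

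The 12-month consequence is smaller and conditional. Conversions on days 61-274 (121-260 with allowances) have no planned contact in the window, which delays ascertainment. The Kaplan-Meier rates suffer only if they are computed before the visit on days 426-639. Primary effectiveness is unaffected and 30-day safety essentially so. The number of subjects concerned cannot be derived from the documents; it is probably small.

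Two broader readings go too far. A reader might infer that converted subjects have no planned renal laboratory data. Tests at discharge and at visits before the conversion are planned, and the Section 8.6 list is not worded as exclusive. What is true is that no laboratory test is listed after conversion. A reader might also infer that every converted subject leaves 5-year follow-up. From about day 1400 onward, the last planned visit falls in or beyond the year-5 window.

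The conclusion assumes that the two-visit schedule replaces the index-timed one. That is the natural reading of Section 8.13, and nothing says otherwise.

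**What to change.** Reconcile Sections 8.6 and 8.13 with Sections 1.0, 9.2.1 and 10.4.1:

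- Keep the two conversion-timed visits. Also keep converted subjects on index-timed contacts at 6 and 12 months and annually to 5 years, for vital status, adverse events and MAE, with Clinical Events Committee adjudication. Telephone contact is enough.
- State in Section 10.4.1 that conversion does not censor mortality or MAE.
- Optionally, say whether serum creatinine is recorded after conversion, since renal failure is an MAE component and no laboratory test is listed there.

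With the index-timed 12-month contact in place, the 214-day band of conversion dates without a contact in days 305-425 closes to 0. Planned contact then reaches year 5 whatever the conversion date. The cost is a wording change and a few extra contacts for what is probably a small number of subjects.

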8.14 Technical Failures

In the event that an AAA stent graft could not be deployed due to a technical failure, contact TriVascular Clinical Affairs to obtain device return information. Device failure information will be captured on the **Device Failure eCRF**.

8.15 Deaths

Any deaths that occur during the conduct of the study must be reported by telephone or fax to the Sponsor **within 24 hours** of knowledge of the event. Sites are also required to adhere to the reviewing IRB requirements for reporting of deaths. In addition, subjects with an implanted device who expire before completing the study should have the device explanted and sent to sponsor whenever possible for examination. Additional information to be submitted to sponsor may include such documents as: death certificate, autopsy report, summary of death report, hospital records, explant reports and copy of IRB notification of the event.

8.16 Explants

Specific instructions for managing the removal, shipping and handling of the explanted device can be found in **Appendix VII: Explant Procedure** and **Manual of Operations**. Explant information will be recorded on the **Explant eCRF**.

9.0 ENDPOINTS AND TECHNIQUES FOR MEASUREMENT

For the purpose of this study, the information below provides definitions and measurement criteria in determining each endpoint. The endpoints (primary and secondary) specified below and Statistical Considerations outlined in Section 10 may appear in the product labeling to support clinical results. Information not included in the endpoint list below or the statistical considerations will not appear in the labeling to support clinical results.

9.1 Primary Endpoints

9.1.1 Safety

The primary safety endpoint is the rate of major adverse events (MAE) at 30 days post procedure. The following specific events will be considered major adverse events:

Major adverse events (MAE) are defined as any one of the following events:

- Death
- Myocardial Infarction
- Stroke (excludes TIA)
- Renal Failure (excludes renal insufficiency)
- Respiratory Failure (excludes COPD or pulmonary complications)
- Paralysis (excludes paraparesis)
- Bowel Ischemia
- Procedural Blood Loss ($\geq 1,000$ cc)

A major adverse event (MAE) may or may not be considered related to the device. Mortality will be reported as “all cause” and “AAA related.” All deaths occurring in the first 30 days post-index procedure are considered “AAA related.”

9.1.2 Efficacy

The primary effectiveness endpoint is the proportion of subjects that achieve treatment success. Treatment success is a composite endpoint assessed at 12 months that requires all of the following criteria to be met in order for a subject to be considered a treatment success:

- Technical Success, defined as successful delivery and deployment of one aortic body and two iliac limbs.
- Freedom from Type I & III endoleak at 12 months
- Freedom from stent graft migration at 12 months
- Freedom from AAA enlargement at 12 months
- Freedom from AAA rupture and conversion to open repair through 12 months

9.2 Secondary Endpoints

9.2.1 Safety

The following secondary safety endpoints will be assessed:

- All-cause mortality at 30 days and 12 months
- AAA Related Mortality at 30 days and 12 months
- Major Adverse Events (MAE) through 12 months
- AAA rupture through 12 months

- Surgical conversion through 12 months

All deaths that occur in the study will be adjudicated by the CEC. AAA related death is any death determined by the CEC to occur as a result of the initial procedure (first 30 days), AAA rupture, conversion to open surgical repair, or any AAA related secondary intervention.

9.2.2 Stent Graft Efficacy

The following secondary efficacy endpoints will be assessed.

1) Technical Success

The physician was able to insert the delivery catheter and deliver an aortic graft and two iliac limbs to the treatment site.

2) AAA Enlargement

Any increase in aneurysm diameter (>5 mm) from the one month (baseline) post-operative measurement will be considered AAA enlargement, as determined by Core Lab.

3) Migration

Migration is defined as evidence of proximal or distal movement of the stent graft >10 mm relative to fixed anatomic landmarks. Spiral CT images will be used by Core Lab to determine migration from the one month (baseline) CT image.

4) Type I and III Endoleak

Type I and III endoleaks will be assessed by the Core Lab using Spiral CT images.

5) Device Integrity

The integrity of the stent graft will be evaluated from X-ray images by the Core Lab using the discharge X-ray as the baseline. Any fractured stents or other issues compromising the integrity of the stent graft will be reported.

9.2.3 Clinical Utility Assessment

The following secondary endpoints associated with the procedure will also be assessed:

- Procedure time
- Amount of blood loss
- Days spent in hospital
- Type of Anesthesia
- Type of Vascular access

10.0 STATISTICAL CONSIDERATIONS

10.1 Primary Endpoints and Hypotheses

10.1.1 Primary Safety Endpoint and Hypothesis: Major Adverse Event Rates

This study is designed to compare the rate of major adverse events following abdominal aortic aneurysm repair with the Ovation Abdominal Stent Graft System to a target performance goal. The proportion of subjects receiving the Ovation Abdominal Stent Graft who experience one or more events meeting the definition of a major adverse event within 30 days of the initial procedure is the rate of interest. The null and alternative hypotheses are given below:

$$H_0: \pi_T \geq 21\%$$

$$H_1: \pi_T < 21\%, \text{ where}$$

π_T is the expected proportion of subjects undergoing AAA repair with the Ovation Abdominal Stent Graft System who experience a major adverse event at 30 days. The target performance goal rate of 21% is that based on the 11% rate (plus 10% "non-inferiority" margin) of major adverse events at 30 days reported for the Medtronic Talent device (reported in the Medtronic Talent Summary of Safety and Effectiveness Data 2008).

10.1.2 Primary Effectiveness Endpoint and Hypothesis: Treatment Success at 12 Months

Treatment success is the primary effectiveness endpoint for the study. The proportion of subjects who are treatment successes at 12 months is the rate of interest. The null and alternative hypotheses are as follows:

$$H_0: \pi \leq 80\%$$

$$H_1: \pi \geq 80\%, \text{ where}$$

π is the expected rate of treatment success. The Ovation Abdominal Stent Graft is considered to be effective if this study's result verifies that the lower limit of the one-sided 95% confidence interval for π is above 80%.

10.2 Statistical Sample Size Justifications for the Primary Study Phase

Should the rate of major adverse events be 11%, n=150 primary study subjects would provide 96% power to test the primary safety hypothesis at the one-sided 5% significance level.

It is anticipated that attrition through the 12 month visit may be approximately 15%. Hence 150 primary study subjects less 15% attrition would yield approximately 130 subjects with data available to assess the primary effectiveness endpoint at 12 months. Should the rate for the primary effectiveness composite endpoint equal 88.2%, then 130 subjects would provide 80% power to test the primary effectiveness hypothesis at the one-sided 0.05 alpha level. Sample size calculations were performed using the normal approximation in nQuery Advisor 6.02.

10.3 Statistical Methods for Primary Endpoints

10.3.1 Primary Safety Endpoint: Major Adverse Events:

Let n be the sample size and $z_{1-\alpha}$ denote the upper $(1-\alpha)$ quantile of the standard normal distribution. If the upper limit of the one-sided confidence interval for the true rate of Major Adverse Events is less than 21%, then the null hypothesis for safety will be rejected in favor of the alternative hypothesis. Therefore, the primary safety endpoint will be considered met if the upper bound of the 95% confidence interval for the measured value is less than the performance goal (21%), based on the major adverse event rate. An accurate estimate of the upper limit of a binomial proportion is presented by Agresti and Coull (Agresti 1998).¹ The Agresti-Coull upper limit of a one-sided 95% confidence interval for the true rate of major adverse events is estimated by Formula 1, where

Formula 1:

$$U = \frac{(2np + Z_{0.05}^2) + Z_{0.05} \sqrt{Z_{0.05}^2 + 4pn(1-p)}}{2(n + Z_{0.05}^2)} \text{, where}$$

p is the observed rate of Major Adverse Events and Z_u is the upper u -th percentile of the standard normal distribution. Hence $Z_{.05} = 1.645$.

10.3.2 Primary Efficacy Endpoint: Treatment Success

Let n be the sample size and $z_{1-\alpha}$ denote the upper $(1-\alpha)$ quantile of the standard normal distribution. If the lower limit of the one-sided confidence interval for the true rate for treatment success is greater than 80%, then the null hypothesis defined in Section 10.1.2 will be rejected in favor of the alternative hypothesis. Using the same approach to calculate the confidence interval as used for the primary safety endpoint, the corresponding formula for the lower limit of the confidence interval is:

Formula 2:

$$L = \frac{(2np + Z_{0.05}^2) - Z_{0.05} \sqrt{Z_{0.05}^2 + 4pn(1-p)}}{2(n + Z_{0.05}^2)} \text{, where}$$

p is the observed rate of treatment success and Z_u is the upper u -th percentile of the standard normal distribution. Hence $Z_{.05} = 1.645$.

